8.1 Primary Efficacy Endpoint and Primary Analysis

The **primary efficacy outcome** of the trial is "time from randomization to *sustained recovery* through Day 90". *Sustained recovery* is defined as being discharged from the index hospitalization, followed by being alive and *home* for 14 consecutive days.

Comment: The shortest possible time to sustained recovery is 14 days (this would require the patient to be discharged from the hospital on the day of randomization), and a patient would have to be discharged from the index hospitalization no later than Day 76 to achieve *sustained recovery* by Day 90.

Definition of *Home* for the primary endpoint:

According to the protocol, section 4.2, *Home* is defined as the level of residence or facility where the participant was residing prior to hospital admission leading to enrollment in this protocol.

Residence or facility groupings to define home are:

- 1) **Independent/community dwelling** with or without help, including house, apartment, undomiciled/homeless, shelter, or hotel
- 2) **Residential care facility** (e.g., assisted living facility, group home, other non-medical institutional setting)
- 3) Other healthcare facility (e.g., skilled nursing facility, acute rehab facility)
- 4) **Long-term acute care hospital** (hospital aimed at providing intensive, longer term acute care services, often for more than 28 days).

Lower (less intensive) level of residence or facility will also be considered as home. By definition, "home" cannot be a "short-term acute care" facility. Participants previously affiliated with a "long-term acute care" hospital recover when they return to the same or lower level of care.

Readmission from "home" (to a higher level of care) may occur and if this occurs within 14 days of the first discharge to "home", then the primary endpoint will not be reached until such time as the participant has been at home for 14 consecutive days.

Participants residing in a facility solely for public health or quarantine purposes will be considered as residing in the lowest level of required residence had these public health measures not been instated.

Primary analysis

The investigational agent will be compared to the (pooled) control group for *time to sustained* recovery through Day 90 by intention-to-treat, using Gray's test with $\rho=0.4$ The test will be

stratified by disease severity at entry and by site pharmacy (as described in section 3 under "stratification"). Gray's test compares the cumulative incidence functions for *sustained recovery* between the treatment groups, taking into account the "competing risk" of death in analyzing *sustained recovery*. Gray's test with ρ =0 is the competing-risks analogue of the log-rank test.

Comments:

- 1. Comparisons will be presented such that recovery rate ratios (RRR) >1 denote superiority of the investigational agent.
- 2. For AZD7442, the primary analysis is hierarchical: the overall comparison between treatment groups is followed by a comparison within the subgroup of participants who are nAb seronegative at study entry (described in Appendix E).

Analyses for the *sustained recovery* endpoint require methods that take into account the competing risk of death, as participants may die before ever achieving *sustained recovery*. The *sustained recovery* outcome requires knowledge of a participant's residence status for at least 14 days after arriving "home" (as defined above).

- The cumulative incidence functions for sustained recovery will be estimated by treatment group, using Aalen-Johansen estimators.³ The estimates will be plotted over time, and tabulated at selected time points (days 15, 21, 28, 42, 60, 75, 90). The Aalen-Johansen estimator for a cumulative incidence function is the analogue of the Kaplan-Meier estimator in the presence of competing risks.
- The recovery rate ratio (RRR) for time to sustained recovery of the investigational agent versus control will be estimated, as a point estimate with a 95% CI, using the Fine-Gray model, stratified by disease severity at study entry and study site pharmacy.^{5,6} The corresponding p-value for RRR=1 versus the two-sided alternative will be calculated. The Fine-Gray method is the competing risks equivalent of Cox proportional hazards models; the RRR compares the cumulative incidence rates of *sustained recovery* between the study arms and is a sub-distribution hazards ratio (sHR).
- To aid in the interpretation of the estimated treatment difference, the median days to sustained recovery (through Day 90) will be estimated for the investigational agent and the control group. Medians will be compared using the Wilcoxon rank sum test or quantile (median) regression. Participants who die at any time up to Day 90 will be assigned 91 days.

Censoring:

- Participants who are alive but have not experienced sustained recovery will be censored at the last date the endpoint status was ascertained (for interim analyses as well as the final analysis).
- For interim monitoring, two sensitivity analyses will be performed:
 - 1. Follow-up for time to sustained recovery will be censored *administratively* at the cut-date for the current report or Day 90, whichever comes first, with last known endpoint status carried forward. For participants who died, this type of censoring is integrated into Gray's test; using a log-rank test would require carrying forward the "not recovered" status for participants who died, up to the administrative censoring date.

2. Administrative censoring as described above will be applied, with the modification that participants who have been discharged from the hospital, were "home" at the latest date when residence was ascertained (but for < 14 days), and, if they have remained there, would have been at home for 14+ days by the cut-date, will be imputed as having experienced *sustained recovery* (achieved on day 14 at home).

Participants who withdrew consent or were lost to follow-up will be censored at the date of withdrawal or the last date the endpoint status was known, respectively.

In the first sensitivity analysis, the "not recovered" status is carried forward to the administrative censoring date; in the second analysis, "sustained recovery" is assumed at the earliest possible date. The first analysis potentially underestimates the rate of recovery, whereas the second analysis overestimates the recovery rate. In all analyses for time to sustained recovery, death is treated as competing risk.

Ascertainment of sustained recovery

The date of discharge from the index hospital will be recorded. Irrespective of the timing of the hospital discharge, there will be patient contact approximately every two weeks, on Days 14, 28, 42, 60, 75, and 90, either at a scheduled clinic visit or through phone contact. At these time points, a) vital status, and b) the location of the participant over time will be recorded, to assess whether the participant had been "at home" for 14 days. Therefore, the outcome status of sustained recovery will usually be ascertained within 3 weeks or less of the date the outcome was achieved.

• To illustrate the status of the primary endpoint, the recovery status of participants will be described over time with the following categories (at interim reviews):

1. At home for 14+ days (reached the primary endpoint of sustained recovery) *Did not reach sustained recovery, and:*

- 2. At home, < 14 days
- 3. Discharged from the hospital, but not at home
- 4. Hospitalized
- 5. Dead
- 6. Primary endpoint status unknown.

The proportions of participants in each of the 6 categories will be summarized over time, by treatment group (stacked bar graphs and tables). In this analysis, both "sustained recovery" and "death" are absorbing states.

Assessment of model assumptions

The trial was powered to detect an RRR of 1.25 with 90% power; this requires 843 sustained recoveries among the 1000 participants by Day 90. The rate of recoveries will be monitored, overall and within the two disease severity strata. Deviations of the observed distribution from the hypothesized distribution in the control arm will be monitored, and the impact on the power of the trial will be assessed. Prior to the completion of the trial for the investigational agent, sample size will be re-estimated by the blinded statisticians on the study team, based on the pooled rate of *sustained recovery*.

• The Fine-Gray model assumes that the sub-distribution rate ratio for *sustained recovery* is constant over time, similar to Cox proportional hazards models. The assumption of constant RRR will be tested by including an interaction effect between time and treatment indicator.

Sensitivity Analyses

- As sensitivity analyses, the primary comparison will be repeated after excluding participants who did not receive any of the investigational agent/placebo (modified intention-to-treat).
- Sensitivity analyses for the primary endpoint comparisons will include consideration of home oxygen above pre-morbid oxygen use (described in section 4.2.2 item 12 of the protocol). For these sensitivity analyses, *sustained recovery* will be re-defined as:
 - a. "Discharged to home, alive at home without use of continuous supplemental oxygen for an uninterrupted 14 day period"
 - b. "Discharged to home, alive at home for an uninterrupted 14 day period, and no supplemental oxygen use a the end of the 14 day period"
- If the RRR is not constant (test described under "assessment of model assumptions" above), as a sensitivity analysis, the RRR will be estimated within time periods, for example, Day 14-28, Day 29-60, Day 61-90.
- Additional sensitivity analyses are described under "censoring" above.

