For the AZD7442 investigational agent, additional subgroup analyses will be carried out for the following subgroups defined at baseline; subgroups, hypotheses and analyses are described in Appendix E:

- SARS-CoV-2 vaccination status. Subgroups will be formed by vaccination status and by type of vaccine.
- Immunosuppressive state
- SARS-CoV-2 viral genome sequence and variant lineage.

As a **general rule**, subgroup analyses will be carried out using statistical models that are stratified by disease severity; for time-to-event analyses, stratified Fine-Gray or Cox proportional hazards models will be used, while for other outcomes, models will include the disease severity indicator as covariate. Global tests for heterogeneity of the treatment effect across subgroups will be carried out, by adding the interaction between the subgroup indicator and the treatment group indicator to a model that contains the treatment group indicator and subgroup variable as "main effects". In case the subgroup was formed by categorizing a continuous variable, the models used for the subgroup analyses will contain the (continuous) subgroup variable as covariate, and the interaction term in the expanded model will be formed between the subgroup indicator and the continuous variable.

Subgroup analyses for the primary endpoint of **time to sustained recovery** will use the Fine-Gray model (with death as competing risk), stratified by disease severity at study entry. Within each subgroup, the number and percent of recovered participants and median time to recovery will be calculated by treatment group, and sHRs with 95% CIs comparing the investigational agent versus control will be estimated. Global tests for heterogeneity of the treatment effect across subgroups will be carried out, by adding the interaction between the subgroup indicator and the treatment group indicator to the model that contains data across all subgroups. Median time to recovery will be estimated using Aalen-Johansen estimators.

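### The supportive median-days comparison scores every death by Day 90 as 91 days, which read literally includes deaths after sustained recovery, and it names tests that cannot use censored times

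*SAP*

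**What the plan says.** All of the following is in SAP section 8.1 unless stated otherwise.

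- **Endpoint.** Sustained recovery "is defined as being discharged from the index hospitalization, followed by being alive and *home* for 14 consecutive days". Nothing is required of the participant after those 14 days.
- **Primary test.** Gray's test, with a Fine-Gray RRR. Both treat death as competing with recovery, and the Censoring text ends by applying that treatment to every time-to-recovery analysis.
- **Median comparison.** Its role is supportive: "To aid in the interpretation of the estimated treatment difference, the median days to sustained recovery (through Day 90) will be estimated". The method is "Medians will be compared using the Wilcoxon rank sum test or quantile (median) regression", and the scoring rule is "Participants who die at any time up to Day 90 will be assigned 91 days".
- **Survivors without recovery.** "Participants who are alive but have not experienced sustained recovery will be censored at the last date the endpoint status was ascertained". Withdrawn and lost participants are likewise censored, at withdrawal or at the last date their status was known.
- **Subgroup medians (section 9.1).** "Median time to recovery will be estimated using Aalen-Johansen estimators".

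Appendix G, which holds the modifications for MP0420, changes none of this.

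**The concern.** There are two separate problems, and they differ in kind.

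The first is a conflict of definition. The 91-day rule is not limited to deaths that precede recovery. The same person can therefore be an early recovery in the primary analysis and a worst-possible outcome in the analysis meant to help interpret it.

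The second is a mismatch of method. An ordinary rank-sum test or median regression needs a usable value for everyone. The bullet supplies one for deaths only, and the Censoring text supplies a censored time for everyone else who did not recover. The analyst would have to choose after the fact: score them beyond Day 90, use the last known day, or leave them out. Using the last known day is the worst of these for early losses. The SAP notes that recovery cannot occur before Day 14, so a participant lost on Day 10 would rank ahead of every true recovery.

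At stake is a supportive p-value and a pair of medians that could differ from the primary result because of coding rather than treatment.

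**Working it through.** **1. The plan's own figure.** The rule has no stated numerical result. The endpoint's design figure does: 843 events for RRR 1.25, 90% power, one-sided 0.025, 1:1 allocation. Schoenfeld's formula gives 4 × (1.960 + 1.282)² / (ln 1.25)² = 844.1, rounded up to 845. Power with 843 events is 0.8996. The figure reproduces within 2 events.

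**2. One participant under each text: recovery on Day 20, death on Day 80.**

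| Analysis | Treatment of this participant |
|---|---|
| Endpoint definition, 8.1 | Recovered |
| Gray's test, Fine-Gray, Aalen-Johansen curve | Event on Day 20; the later death plays no part |
| Median comparison, 8.1, read literally | 91 |
| Table E-1 (AZD7442), which lists deaths before recovery only | Recovered |

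The interim status display in 8.1 also treats recovery as absorbing ("In this analysis, both 'sustained recovery' and 'death' are absorbing states"). That sentence is limited to the display, so it is only weak support.

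**3. How many people have no value under the rule.** The only outcome split in the documents is Table E-1, pooled over arms, from the sister AZD7442 trial (1,417 infused):

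- Recovered: 1,195 (84.3%). Died before recovery: 138 (9.7%).
- Alive and unrecovered: 12 + 14 + 25 = 51 (3.6%).
- Status unknown: 6 + 23 + 4 = 33 (2.3%).

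The 51 have a known status and would naturally rank beyond Day 90. Only the 33 are a true missing-value problem. Deaths after recovery cannot be read from the table.

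**4. Effect on the medians and the test.** This is a simulation of 3,000 trials per scenario with a two-sided 5% Wilcoxon test.

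- From the documents: RRR 1.25; control recovery 84.3%; 240 per arm (485 infused for MP0420, Appendix G); 62% of the unrecovered die (138 / (1,417 − 1,195) = 138/222).
- Assumed: the shape of the recovery-time curve (control median about 21.5 days); 0 to 5% of recovered participants dying later; last-known days.

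| Scoring | Median, control / active (days) | Power |
|---|---|---|
| No later deaths; survivors scored 91 | 21.55 / 19.84 | 0.543 |
| No later deaths; survivors at last known day | 21.53 / 19.84 | 0.533 |
| No later deaths; survivors left out | 20.80 / 19.50 | 0.428 |
| Later deaths 1% in each arm, scored 91 | 21.65 / 19.92 | 0.530 |
| Later deaths 2% in each arm, scored 91 | 21.80 / 20.02 | 0.542 |
| Later deaths 5% in each arm, scored 91 | 22.24 / 20.34 | 0.488 |
| Later deaths 2% control, 4% active, scored 91 | 21.80 / 20.22 | 0.382 |

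Keeping the recovery day for later deaths gives 21.5 / 19.8 days and power of 0.54 to 0.56 throughout. The Monte Carlo standard error is about √(0.54 × 0.46 / 3,000) = 0.009, so the 1% and 2% balanced rows differ little from that reference.

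The largest shift in a median is 22.24 − 21.52 = 0.72 day from the literal death rule (5% row), and 21.55 − 20.80 = 0.75 day from leaving survivors out. That last row removes every unrecovered survivor, including those whose status is known, so it is an extreme choice.

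**The case against.** The strongest reply has three parts.

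- **It is loose drafting.** The section says death is a competing risk in all time-to-recovery analyses, so the 91-day sentence was probably meant for deaths before recovery. That may be so, but the sentence as written says otherwise, and a programmer will follow the sentence.
- **It may be deliberate.** Section 8.3 gives a value of 0 days alive outside hospital to anyone who dies within 90 days, so a death penalty has a precedent in this SAP. A death-penalised composite is legitimate. Section 8.3, however, gives its reason, by reference to practice in intensive-care trials. Section 8.1 gives none and calls the result days to sustained recovery.
- **The right method is already in the plan.** Section 3 names competing-risk methods for this endpoint, 8.1 estimates Aalen-Johansen curves, and 9.1 takes medians from them. This stands. It makes the remedy nearly free, and it leaves no reason for the overall comparison to use tests that do not accept censoring.

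It is also true that the comparison is only an aid to interpretation, and that balanced later deaths of 1 to 2% barely change anything.

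**Conclusion.** The point holds as a minor correction to a supportive analysis. The 91-day rule, read literally, conflicts with the endpoint definition and with the competing-risk treatment of death. The named tests do not fit the censoring that the section prescribes. Gray's test and the Fine-Gray RRR are unaffected, and the medians move by at most about 0.7 to 0.8 day in the scenarios examined. Wilcoxon power can shift by about 0.11 with the handling of survivors, and by about 0.17 if later deaths are unbalanced between arms. Both shifts rest on assumed inputs.

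A reader might infer three stronger things that the documents do not support:

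- **That the median analysis as a whole contradicts the primary endpoint.** Only the scoring of deaths after recovery conflicts with it. Scoring deaths before recovery as 91 is consistent with never recovering. The missing value for survivors is a gap in specification.
- **That the Wilcoxon test has an inflated false-positive rate.** That needs lost participants to be ranked by follow-up time, which the SAP does not prescribe, together with early loss that differs between arms. No document gives loss by arm or by timing. For MP0420, the 9 participants who withdrew before infusion are already outside the mITT population.
- **That all 84 participants without recovery or known death in Table E-1 are a missing-data problem.** 51 of them were known to be alive and unrecovered, and the table belongs to another agent's trial.

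**What to change.** In section 8.1, before unblinding:

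1. Keep the observed recovery day for anyone who reached sustained recovery, whatever happens later. Limit 91 to deaths before recovery and to survivors known to be unrecovered at Day 90.
2. Take the medians, with confidence intervals, from the Aalen-Johansen curves already estimated in 8.1, as 9.1 does for subgroups. Participants censored early then contribute their censored time and are not ranked by length of follow-up.

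If the penalty for any death by Day 90 is intended, keep it as a separately labelled death-penalised composite with its reason stated, and say how participants censored before Day 90 are scored.

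The cost is about two sentences in section 8.1. No new data are needed, and the primary analysis does not change.

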1.2 Description of the Study Design

This section is adapted from Section 1 of the TICO protocol versions 2.0 and 3.0.

Design

TICO is a master protocol to evaluate the safety and efficacy of multiple investigational agents aimed at modifying the host immune response to severe acute respiratory syndrome coronavirus 2 (SARS-CoV-2) infection, or directly enhancing viral control in order to limit disease progression.

Trials within this protocol will be adaptive, randomized, blinded and initially placebocontrolled. Participants will receive standard of care (SOC) treatment as part of this protocol. If an investigational agent shows superiority over placebo, SOC for the study of future investigational agents may be modified accordingly.

The protocol is for a phase III randomized, blinded, controlled platform trial that allows investigational agents to be added and dropped during the course of the study for efficient testing of new agents against control (i.e., placebo + SOC) within the same trial infrastructure. When more than one agent is being tested concurrently, participants will be randomly allocated across agents (as well as between the agent and its placebo). For analysis, placebo groups of concurrently randomized agents will be pooled; therefore, control groups may overlap for different agents.

Randomization will be stratified by study site pharmacy and disease severity. There are 2 disease severity strata, defined as below:

- **Disease severity stratum 1:** Absence of all of the following: stroke, meningitis encephalitis, myelitis, myocardial infarction, myocarditis, pericarditis, symptomatic congestive heart failure (NYHA class III or IV), arterial or deep venous thrombosis or pulmonary embolism, requirement for invasive mechanical ventilation, ECMO, mechanical circulatory support, vasopressor therapy, or new renal replacement therapy.
- **Disease severity stratum 2:** Presence of at least one of the excluded conditions or treatments in disease severity stratum 1.

The **primary endpoint** is the time from randomization to sustained recovery, defined as being discharged from the index hospitalization, followed by being alive and home for 14 consecutive days prior to Day 90. The definition of home will be operationalized as the level of residence or facility where the participant was residing prior to hospital admission leading to enrollment in this protocol.

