The following baseline characteristics will be reported; unless noted otherwise, categorical variables will be summarized with numbers (%) in each category, and continuous variables will be summarized with median (IQR); in the open report, in addition, the mean (SD) and range may be provided. When enrolment has been completed, frequency distributions of these characteristics, including cut points for discretizing continuous measures, will be considered for defining subgroups in the final report.

- Demographics
 - Age: distribution in categories 18-29, 30-39, 40-49, 50-59, 60-69, 70-79, ≥80 years; and summary as continuous variable
 - Sex at birth: number (%) male, female
 - Ethnic group: number (%) Asian, Black, Latino/Hispanic, White, other
 - Type of residence ("home")
 - Country of enrolment
- COVID-19 related characteristics
 - Duration of symptoms prior to enrolment
 - Use of remdesivir prior to enrolment
 - Pulmonary and pulmonary+ ordinal outcomes, number (%) in each category
 - NEWS: summary as continuous variable
 - Respiratory function scale (modified Borg dyspnea scale; continuous outcome)

- Disease severity randomization stratum (for investigational agents that enrol in both strata), number (%) in each category
- Receipt of SARS-CoV-2 vaccination, and type of vaccine (and if received as part of a blinded clinical trial, in which case the vaccine may be active or control)
- Other clinical characteristics
 - Concomitant treatments
 - Corticosteroid use will be summarized overall, and separately by oxygen requirement at baseline (no supplemental oxygen, < 4 L/min, conventional supplemental oxygen > 4 L/min, high-flow oxygen or mechanical ventilation/ECMO)
 - History of chronic conditions (cardiovascular disease, diabetes, asthma, chronic obstructive pulmonary disease, hypertension, chronic kidney disease, hepatic impairment, cancer, or immunosuppressive disorder [HIV, and other than HIV])
 - Prior cerebrovascular event
 - Prior myocardial infarction (MI)
 - Requirement of continuous chronic supplemental oxygen
 - BMI (<30, 30-39.9, 40+)
 - Pregnancy (not applicable to protocol versions 2 and 3)
- Laboratory values: as continuous outcomes, and number (%) of grade 3 or 4 abnormalities according to the DAIDS AE Grading Table.

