Appendix A. Definition of the Pulmonary and Pulmonary+ ordered categorical outcomes

The Pulmonary categorical outcome is primarily defined based on oxygen requirements. The categories of the Pulmonary+ outcome are similar, except that categories 4 and 5 also capture selected extra-pulmonary complications, highlighted in red below.

Pulmonary outcome	Pulmonary+ outcome
1. Can independently undertake usual activities with minimal or no symptoms	1. Can independently undertake usual activities with minimal or no symptoms
 Symptomatic and currently unable to independently undertake usual activities but no need of supplemental oxygen (or not above premorbid requirements) 	2. Symptomatic and currently unable to independently undertake usual activities but no need of supplemental oxygen (or not above premorbid requirements)
 Supplemental oxygen (<4 liters/min, or <4 liters/min above premorbid requirements) 	 Supplemental oxygen (<4 liters/min, or <4 liters/min above premorbid requirements)
 Supplemental oxygen (≥4 liters/min, or ≥4 liters/min above premorbid requirements, but not high-flow oxygen) 	 4. Supplemental oxygen (≥4 liters/min, or ≥4 liters/min above premorbid requirements, but not high-flow oxygen) or any of the following: stroke (NIH Stroke Scale [NIHSS] ≤14), meningitis, encephalitis, myelitis, myocardial infarction, myocarditis, pericarditis, new onset CHF NYHA class III or IV or worsening to class III or IV, arterial or deep venous thromboembolic events
 Non-invasive ventilation or high-flow oxygen 	 Non-invasive ventilation or high-flow oxygen, or signs and symptoms of an acute stroke (NIHSS >14)
 Invasive ventilation, extracorporeal membrane oxygenation (ECMO), mechanical circulatory support, or new receipt of renal replacement therapy Death 	 Invasive ventilation, ECMO, mechanical circulatory support, new receipt of renal replacement therapy, or vasopressor therapy Death

The term "usual activities", in categories 1 and 2 for both outcomes, refers to activities of daily living that the participant was able to undertake prior to the current illness.

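### The two home-oxygen sensitivity definitions of sustained recovery omit the pre-morbid qualifier that their own introduction states (internal inconsistency, minor)

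*SAP*

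**What the plan says.** The primary endpoint is "being discharged from the index hospitalization, followed by being alive and home for 14 consecutive days prior to Day 90" (SAP section 1.2; section 8.1 is to the same effect). It has no oxygen criterion.

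The sensitivity analyses in section 8.1 add one. The introductory sentence gives the purpose: "Sensitivity analyses for the primary endpoint comparisons will include consideration of home oxygen above pre-morbid oxygen use", and points to its source as "described in section 4.2.2 item 12 of the protocol". Sustained recovery is then re-defined in two ways:

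- (a) "Discharged to home, alive at home without use of continuous supplemental oxygen for an uninterrupted 14 day period"
- (b) discharged and alive at home for 14 uninterrupted days, with "no supplemental oxygen use a the end of the 14 day period" (the slip in the wording is in the SAP and is only typographical).

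Two other places bear on this. SAP section 5 (Baseline Characteristics) lists "Requirement of continuous chronic supplemental oxygen" among the items to be reported, so chronic users are expected in the trial. In Appendix A, category 2 of both ordinal outcomes carries the qualifier in its own definition: "no need of supplemental oxygen (or not above premorbid requirements").

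**The concern.** The introduction limits the analyses to oxygen beyond what the participant used before COVID-19. The definitions that replace the endpoint apply an absolute standard instead. A participant who was on continuous oxygen before admission and goes home on the same oxygen has no oxygen use above the pre-morbid level, yet fails (a) and (b) on every day to Day 90. An intermittent user may pass (a) and fail only (b).

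The analyses exist to test whether the primary result survives when recoveries that still need COVID-related oxygen are not counted. Taken literally, they also discard complete returns to the pre-illness state among people with chronic oxygen need. A lower recovery proportion or a shifted RRR could then not be put down to residual COVID-19 oxygen need alone. Two programmers, one following the introduction and one the definitions, could also produce different results from the same data.

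**Working it through.** **Texts side by side**

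| Place in SAP | Oxygen standard | Relative to pre-morbid use? |
|---|---|---|
| 8.1, introduction to the sensitivity analyses | home oxygen above pre-morbid use | Yes |
| 8.1, definition (a) | no continuous oxygen for 14 days | No |
| 8.1, definition (b) | no oxygen at the end of 14 days | No |
| 1.2 and 8.1, primary endpoint | none | Not applicable |
| Appendix A, category 2 | none, or none above pre-morbid | Yes |

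No exception for chronic users appears elsewhere in the supplied text.

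**The plan's own figure.** Section 1.2 requires 843 events for 90% power at RRR 1.25, one-sided 0.025, with 1:1 allocation. Schoenfeld: 4(1.960 + 1.282)² / (ln 1.25)² = 845 events. Power at 843 events is Φ(½·√843·ln 1.25 − 1.960) = 0.900. The figure reproduces, and this point does not dispute it.

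**Fixed non-events.** Appendix G gives 485 infused participants (mITT). Prevalence of chronic continuous oxygen is an assumption, shown over a range. The planned recovery proportion is 843/1000 = 84.3%, taken to be the same in chronic users.

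| Assumed prevalence | Fixed non-events, 485 × p | Recoveries lost, × 0.843 |
|---|---|---|
| 1% | 4.9 | 4.1 |
| 3% | 14.6 | 12.3 |
| 5% | 24.3 | 20.4 |

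**Comparison with real non-recovery.** In Table E-1 (AZD7442), 12 + 14 + 25 = 51 participants were alive and known not to have recovered. The total of 1417 includes 6 + 23 + 4 = 33 who withdrew or had unknown status, so known status is 1417 − 33 = 1384, and 51/1384 = 3.7%. Applied to 485 this gives 17.9 (17.5 if 1417 is the denominator), or about 17–18. The forced non-events are below this at 1%, somewhat below it at 3%, and above it only at 5%.

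**Effect on precision.** If 5% of the 843 planned events were lost (42), about 801 remain. Power at RRR 1.25 would fall from 0.900 to 0.884.

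**Effect on the RRR.** Assume control recovery of 82% by Day 90 and a true RRR of 1.25. Active recovery is then 1 − 0.18^1.25 = 88.3%; the average of the two arms, 85.1%, is close to the planned 84.3%. Removing a fraction p of recoveries in both arms multiplies each cumulative incidence by (1 − p). The large-sample Fine-Gray estimate, with censoring only at Day 90, is then 1.24, 1.23 and 1.22 for p = 1%, 3% and 5%. A hand check at p = 5% uses the Day 90 incidences 0.779 and 0.839: ln(1 − 0.839)/ln(1 − 0.779) = 1.21. This is lower than 1.22 because it takes the cumulative ratio at Day 90, where the attenuation is greatest, whereas the model averages over follow-up.

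**The case against.** The strongest reply is that the introduction governs. It sets the scope, (a) and (b) are its sub-items, and a careful programmer would carry the qualifier down. The definitions also stand in quotation marks next to a reference to master protocol section 4.2.2 item 12. The supplied protocol is only the MP0420 appendix (H5), so that item cannot be read here, and it may hold the qualifier or a rule for chronic users.

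Part of this stands. It lowers confidence, and a reader who infers that chronic users definitely will be scored as never recovered goes further than the documents allow. It does not remove the inconsistency: it concedes that the intended meaning is oxygen above pre-morbid use, and the definitions that replace the endpoint do not say so.

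The objection that the effect is small also stands. Chronic oxygen is a baseline trait under blinded randomization, and section 5 has baseline characteristics summarized by treatment group in the closed reports, so an imbalance would be visible there.

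Three stronger readings are tempting and are not supported:

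- *Appendix A counts oxygen up to 4 L/min above pre-morbid as back to baseline.* It does not; that is category 3, a supplemental-oxygen state. The relevant parallel is the qualifier in category 2, which itself describes a participant who is still symptomatic.
- *Forced non-events would outnumber genuine unrecovered survivors.* That holds only at the top of an assumed range, against a rate borrowed from another agent's trial.
- *The trial's main result is at risk.* The primary endpoint has no oxygen criterion.

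**Conclusion.** The definitions are wrong as written: they contradict the purpose stated in the same bullet. Severity is minor and confidence moderate, the latter because item 12 of the master protocol was not supplied.

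The consequence is confined to two sensitivity analyses. It is a lower recovery proportion in both arms, some lost precision, and a slight attenuation of the RRR, from 1.25 to between about 1.24 and 1.22 for 1% to 5% chronic use. No arm is favoured. These sizes rest on an assumed prevalence, on chronic users recovering at the same rate as others, on equal prevalence in the two arms, and on 82% control recovery. The documents give none of these except the planned overall recovery proportion.

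**What to change.** In section 8.1:

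1. Add the words *above the pre-morbid requirement* after the reference to oxygen in both (a) and (b), in line with category 2 of Appendix A.
2. Name the baseline chronic-oxygen item in section 5 as the reference.
3. State how pre-morbid intermittent users are handled under (b), because the baseline item covers only continuous need.
4. Reconcile the wording with master protocol section 4.2.2 item 12.

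The cost is a line or two of SAP text. The continuous-oxygen item is already listed for collection at baseline, and section 1.1 already provides for SAP updates before each agent is unblinded. Section 8.1 is common to all agents, so one change serves the platform.
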